#### 10.1.5 **Pregnancy Reporting**

To ensure subject safety, each pregnancy occurring while the subject is on study treatment must be reported to ITB-MED Safety within 24 hours of learning of its occurrence. The pregnancy should be followed to determine outcome, including spontaneous or voluntary termination, details of the birth, and the presence or absence of any birth defects, congenital abnormalities, or maternal and/or newborn complications.

Pregnancy follow-up should be reported to ITB-MED Safety and should include an assessment of the possible relationship to the investigational treatment to pregnancy outcome. Any AE or SAE experienced during pregnancy must also be reported.

#### 10.1.6 Early Phase Safety Monitoring

The Investigator will monitor AEs in an ongoing manner and inform ITB-MED of any clinically relevant observations. Any required safety reviews will be made jointly between medically qualified personnel between ITB-MED or it's designee and the Investigator(s). Criteria pertaining to stopping the study/treatment or adapting the study design are presented above.

ITB-MED will advise the Investigator(s) at all sites in writing (e-mail) (and by telephone if possible) of any new, clinically relevant safety information during the conduct of the study in a timely manner.

#### **Reporting of Study Treatment Errors** 10.1.7

Medication errors are defined as potential, intercepted, or unintentional errors in the prescribing, dispensing, administration, or monitoring of a medicine while under the control of a healthcare professional, subject, or consumer.

Study treatment errors and uses outside of what is foreseen in the protocol will be recorded on the appropriate eCRF irrespective of whether or not associated with an AE/SAE and reported to Safety only if associated with an SAE; however, the ITB-MED study team should be notified immediately.

### 11 **Data Monitoring Committee**

This study will include a DMC which will function independently of all other individuals associated with the conduct of this clinical trial, including the site investigators participating in the study. The DMC will assess at defined intervals the progress of the clinical trial, safety data, and critical efficacy variables and recommend to ITB-MED whether to continue, modify or terminate a trial.

Specific details regarding composition, responsibilities, data monitoring and meeting frequency, and documentation of DMC reports, minutes, and recommendations will be described in a separate charter that is established between ITB-MED and the DMC.

# 12 Data Analysis and Statistical Methods

This section describes the statistical methods to be used to analyze safety and efficacy. These methods may be revised and updated due to reasons such regulatory requirements or need for further clarifications.

The final analysis plan will be documented in a formal statistical analysis plan (SAP) that must be finalized before database lock. The SAP will include details on how variables will be derived, how missing data will be handled, and how data will be presented as well as the details on statistical methods to be used for safety and efficacy analyses. The final Clinical Study Report (CSR) will discuss deviations from the SAP, if any.

Any data analysis carried out independently by the investigator must be submitted to ITB-MED before publication or presentation.

# 12.1 Analysis sets

The Full Analysis Set (FAS) comprises all subjects to whom study treatment has been assigned by randomization. According to the intent to treat principle, subjects will be analyzed according to the treatment they have been assigned to during the randomization procedure.

The Safety Set includes all subjects who received at least one dose of study treatment. Subjects will be analyzed according to the study treatment received, where treatment received is defined as the randomized/assigned treatment if the subject took at least one dose of that treatment or the first treatment received if the randomized/assigned treatment was never received.

The PK Analysis Set will include all subjects with at least one available valid (i.e., not flagged for exclusion) PK concentration measurement, who received any study drug and experienced no protocol deviations with relevant impact on PK data.

The PD Analysis Set will include all subjects in the Full Analysis set with available PD data and no protocol deviations with relevant impact on PD data.

For all analysis sets, subjects will be analyzed according to the study treatment(s) received.

# 12.2 Subject Demographics and other Baseline Characteristics

All data for background and demographic variables will be listed by treatment group and subject. Summary statistics will be provided by treatment group.

Subject demographics will include age, sex, race, ethnicity, height, weight and BMI. Other baseline disease characteristics include relevant medical history, current medical conditions,

Page 79 of 117 Confidential

results of laboratory screens, transplant history, donor characteristics (e.g., age, sex, race, type, CIT) and any other relevant information.

Summary statistics will be presented for the subjects in the FAS. Continuous variables will be presented with mean, median, 25th percentile, 75th percentile, standard deviation (SD), minimum and maximum, and the number of non-missing observations.

Categorical data will be displayed via absolute and relative frequencies for each category (including a category labeled as "missing" when appropriate).

#### 12.3 **Treatments**

The duration (days) of study medication administration will be summarized. This will be calculated by subtracting the date of the last administration of study medication from the date of first administration and then adding the dosing interval for siplizumab, TAC, MMF or CS. In calculating the duration of treatment, days of temporary interruption of study medication for any reason will be included. Further, the frequency of dose changes (including temporary dose interruption) will be presented by reason for the change.

Average daily doses will be presented by treatment. "Zero" will be used for periods of temporary interruption of study medication for any reason.

The number and percentage of subjects who prematurely discontinued study medication will be summarized by reason for discontinuation.

Study treatment errors, including uses outside of what is foreseen in the protocol will be summarized. AEs as a result of study treatment error will also be summarized.

#### 12.3.1 **Concomitant Immunosuppressants**

The average daily dose of administered TAC, MMF, and CS will be summarized by treatment arm for subjects on study medication. The dose of the induction agent will be summarized for each of days when it was administered.

The dose of antibodies used for the treatment of acute rejection episodes will be recorded as well.

#### 12.3.2 Other Co-Medications

Concomitant medications, other than immunosuppressants and CS mentioned above, will be summarized by therapeutic class and preferred term by presenting the number and percentage of subjects using each medication for each treatment group.

### 12.4 **Analysis of the Primary Endpoint(s)**

#### 12.4.1 **Definition of Primary Endpoint(s)**

All safety data, including laboratory assessments, vital signs and AEs are considered primary endpoints.

All information obtained on AEs will be displayed by treatment and subject. The number and percentage of subjects with AEs will be tabulated by body system and preferred term with a breakdown by treatment arm. A subject with multiple AEs within a body system is only counted once towards the total of this body system. No formal statistical analysis will be done for the safety and tolerability evaluation.

# 12.4.2 Statistical Model, Hypothesis, and Method of Analysis

All data will be summarized and presented descriptively, no formal statistical analysis or hypothesis testing will be conducted on the analysis sets.

The use of the concurrent control group and supplementation with a historical control group to better assess the incidence of AEs and SAEs reported with a TAC/MMF/CS based SoC treatment regimen will be investigated. Details on the methodology for data selection and analysis will be presented in the SAP.

# 12.4.3 Handling of Missing Values/Censoring/Discontinuations

The analysis will be made on the FAS population. The following imputation method will be applied for subjects with missing data:

- Patients that lose their graft will be assigned a value of zero for their missing estimated glomerular filtration (eGFR) value.
- Patients that die or are lost to follow-up with a functioning graft will have an imputed value using the last-observation-carried-forward (LOCF) method.
- For subjects that discontinue randomized treatment, the eGFR will be considered missing after applying the windows defined in Section 12.1.

Graft loss subjects do not have a functioning graft; hence the lowest possible GFR value (zero) will be assigned to such subjects. In contrast, subjects that die with a functioning graft, die for different reasons (e.g., suicide, car accident, cancer) will have an imputed value assigned as described above.

Patients who are lost to follow-up have renal function, but missing values for various reasons (e.g., moving from the area or not being able to make the site visit during the Month 6 or Month 12 visit window). Patients who have a functioning graft at the time of death or are Lost to Follow-up with a functioning graft will be analyzed via an imputation method that employs LOCF.

# 12.5 Analysis of Secondary Endpoints

# 12.5.1 Efficacy and/or Pharmacodynamic endpoint(s)

# Immunophenotyping

These data will be summarized by treatment and subject.

# **CD2 Receptor Occupancy**

The magnitude and duration of PD effect of siplizumab will be as measured by peripheral blood CD2-receptor occupancy. These data will be summarized by treatment and subject. Descriptive

statistics will also be provided such as mean, median, SD, minimum and maximum, by time point and treatment.

#### 12.5.2 Safety Endpoints

For all safety analyses, the safety set will be used. All listings and tables will be presented by treatment group.

Safety summaries (tables, figures) include only data from the on-treatment period with the exception of baseline data which will also be summarized where appropriate (e.g., change from baseline summaries). In addition, a separate summary for death including on treatment and post treatment deaths will be provided. In particular, summary tables for AEs will summarize only on-treatment events, with a start date during the on-treatment period (treatment-emergent AEs).

The on-treatment period lasts from the date of first administration of study treatment through the month 12 or EOS visit.

### **Adverse Events**

All information obtained on AEs will be displayed by treatment group.

The number (and percentage) of subjects with treatment emergent AEs (events started after the first dose of study medication or events present prior to start of treatment but increased in severity based on preferred term) will be summarized in the following ways:

- AEs by primary System Organ Class (SOC) and Preferred Term
- AEs rated to have relationship to study drug by SOC and Preferred Term
- AEs by primary SOC, Preferred Term, and maximum severity
- SAEs by SOC and Preferred Term
- SAEs rated to have relationship to study drug by SOC and Preferred Term
- Deaths by SOC and Preferred Term
- AEs leading to discontinuation of a study drug by SOC and Preferred Term
- AEs leading to dose adjustment or interruptions of a study drug by SOC and Preferred Term
- Infections by type of infection (viral, bacterial, fungal, and others) and microorganism of infection
- Serious infections by type of infection and micro-organism of infection
- AEs by standardized MedDRA query (SMQ) levels (broad and narrow search)
- AEs by SMQ and Preferred Term (broad and narrow search)

Separate summaries will be provided for study medication related AEs, death, SAEs, other significant AEs leading to discontinuation and AEs leading to dose adjustment.

Page 82 of 117 Confidential

The number (and proportion) of subjects with AEs of special interest/related to identified and potential risks (e.g., serious infections, opportunistic infections, cytokine release syndrome, malignancies) will be summarized by treatment.

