### 10.1.3 Adverse Events of Special Interest

The following AEs are selected as adverse events of special interest (AESI) for surveillance and follow-up, both serious and non-serious, based on previous experience with siplizumab, all:

- Serious Infections
- Opportunistic Infections, including EBV, CMV, BK virus
- Malignancies, including LPD/PTLD

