### 3. INTRODUCTION

This statistical analysis plan (SAP) is based on Protocol TCD601B102, Version 2.0 dated 02-Mar-2022 for Study TCD601B102.

The purpose of this document is to provide details on the analysis populations and on derivation of the variables, handling of missing data, as well as detailing the statistical methodologies to be used to analyze the safety and efficacy data for the final analysis.

This is the final SAP, and is approved by the Sponsor, and filed within the TMF before the final database is locked. The approved plan will be used to carry out all analyses for the final analysis. Deviations, if any, from the approved plan will be noted in the clinical study report.

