#### **10.1.2. Adverse Events**

Each AE and SAE term will be recorded as a verbatim term on the case report forms (CRFs). All AEs and SAEs will be coded by primary system organ class (SOC) and mapped to a preferred term using the MedDRA dictionary (version 26.0 or higher). The investigator will assess AE severity and relationship to the study treatment.

All AEs will be listed. However, only treatment emergent adverse events (TEAEs) will be included in the AE summaries. A TEAE is defined as any AE with an onset date on or after the first study treatment dosing date. In addition, any AEs that the investigators deem to be treatment related, regardless of onset date, will also be considered TEAEs and will be included in the AE summaries.

For the purpose of calculating treatment emergence and inclusion in summary tables, incomplete onset dates will be imputed using the method described in Appendix A.

AEs will be summarized by the number and percentage of subjects in each primary SOC and preferred term. Subjects will be counted only once for each primary SOC and each preferred term. Summary tables of AEs by primary SOC, preferred term and severity will be provided. If a subject has more than one AE coded to the same preferred term, the subject will be counted only once for that preferred term by using the event with the highest severity. Similarly, if a subject has more than one AE within a primary SOC category, the subject will be counted only once in that SOC category by using the event with the highest severity. AEs by primary SOC, preferred term and relationship to study drug will be provided as well. If a subject has more than one AE coded to the same preferred term, the subject will be counted only once for that preferred term by using the most related event. Similarly, if a subject has more than one AE within a primary SOC category, the subject will be counted only once in that primary SOC category by using the most related event. In addition, serious adverse events (SAEs) by primary SOC and preferred term will be provided. Deaths and SAEs will be summarized similarly to AEs. All adverse event tables will also include the total number of events, counting multiple events per subject.

In the AE summary, preferred terms within each SOC will appear in alphabetical order.

Frequencies for deaths and hospitalizations will also be summarized by treatment group and overall.

All information obtained on AEs will be displayed by treatment group.

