The number (and percentage) of subjects with treatment emergent AEs (events started after the first dose of study medication or events present prior to start of treatment but increased in severity based on preferred term) will be summarized in the following ways:

- AEs by primary System Organ Class (SOC) and Preferred Term
- AEs rated to have relationship to study drug by SOC and Preferred Term
- AEs by primary SOC, Preferred Term, and maximum severity
- SAEs by SOC and Preferred Term
- SAEs rated to have relationship to study drug by SOC and Preferred Term
- Deaths by SOC and Preferred Term
- AEs leading to discontinuation of a study drug by SOC and Preferred Term
- AEs leading to dose adjustment or interruptions of a study drug by SOC and Preferred Term
- Infections by type of infection (viral, bacterial, fungal, and others) and microorganism of infection
- Serious infections by type of infection and micro-organism of infection
- AEs by standardized MedDRA query (SMQ) levels (broad and narrow search)
- AEs by SMQ and Preferred Term (broad and narrow search)

Separate summaries will be provided for study medication related AEs, death, SAEs, other significant AEs leading to discontinuation and AEs leading to dose adjustment.

All AEs will be presented in individual by-subject data listings. Listings of any subject experiencing TEAEs related to study drug, and an SAE will be provided separately.

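### The SAP omits the protocol's by-arm summary of special-interest and key-risk adverse events and defines no grouping for opportunistic infection or malignancy/LPD/PTLD

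*Protocol*

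**What the plan says.** **Protocol.** Section 10.1.3 defines the special-interest events: "The following AEs are selected as adverse events of special interest (AESI) for surveillance and follow-up, both serious and non-serious". It lists three groups: serious infections; opportunistic infections, with EBV, CMV and BK virus named; and "Malignancies, including LPD/PTLD". Cytokine release syndrome is not among them. Section 10.1.4 requires these events to be reported by the same route as SAEs, whether serious or not.

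Section 12.5.2, under Adverse Events, gives twelve bulleted summaries and a sentence on separate summaries. It then adds a further commitment: "The number (and proportion) of subjects with AEs of special interest/related to identified and potential risks", continuing with "e.g., serious infections, opportunistic infections, cytokine release syndrome, malignancies) will be summarized by treatment".

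**SAP.** Section 3 ties the plan to the protocol version that contains this commitment ("This statistical analysis plan (SAP) is based on Protocol TCD601B102, Version 2.0 dated 02-Mar-2022") and states: "The approved plan will be used to carry out all analyses for the final analysis". Section 10.1.2 has the same twelve bullets, followed by "Separate summaries will be provided for study medication related AEs, death, SAEs, other significant AEs leading to discontinuation and AEs leading to dose adjustment". The next text concerns by-subject listings, and the special-interest summary is absent. The readable SAP does not mention special-interest events anywhere, including its abbreviation list, and gives no reason for the omission.

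**The concern.** Opportunistic infection and lymphoproliferative disease are composites: one risk can be recorded under several terms. A table by preferred term splits such a risk into small rows, and with 8 subjects per arm most rows will hold 0 or 1. A reader who wants to know how many subjects in each arm had at least one opportunistic infection, or any malignancy including LPD/PTLD, would find no row that says so.

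The protocol treats these as risks to watch. They appear in 4.5.1 and 10.1.3, and histologically confirmed EBV-PTLD and Grade 3 or higher cytokine release syndrome are stopping criteria in 9.1.1. Section 4.2 justifies the rATG arm partly by the comparative safety data it will supply. If the grouping is chosen only after the data are seen in an open-label trial, the choice of terms can move the by-arm count.

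**Working it through.** No design figure is at issue. The check compares the two texts and then tests whether the retained tables can replace the missing one.

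**1. Protocol 12.5.2 against SAP 10.1.2**

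| Item in protocol 12.5.2 | In SAP 10.1.2? |
|---|---|
| Twelve bulleted adverse event summaries | Yes, 12 of 12 |
| Sentence on separate summaries | Yes |
| By-treatment summary of special-interest and key-risk events | No |

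**2. Could it sit elsewhere in the SAP?** Section 12 is largely redacted, but its headings can be read in the table of contents: immunogenicity, BK, EBV (twice), renal function, a CD2 assay, biomarkers and CMV. None is a special-interest, malignancy or cytokine release summary. The BK, EBV and CMV sections may hold counts for those viruses, which cannot be checked.

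**3. What the retained tables give for each named group**

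| Group | Retained in the SAP | What is missing |
|---|---|---|
| Serious infections | Own table, by type and organism | Little |
| Cytokine release syndrome | Countable as a preferred term | Little, if coded to one term |
| Malignancy incl. LPD/PTLD | SOC and preferred-term rows; SMQ tables with no SMQ named | A defined group that joins the labels |
| Opportunistic infection | Infections by type and organism; SOC and preferred-term rows; SMQ tables with no SMQ named | Any definition of the group |

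**4. Can the group count be rebuilt from rows?** Protocol Table 4-1 has both a composite row and its preferred-term rows.

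| | ≤ 0.12 mg/kg (n=13) | > 0.12 mg/kg (n=10) | Total (N=23) |
|---|---|---|---|
| Sum of rows | 0+1+0+1+0+0 = 2 | 2+1+1+0+1+1 = 6 | 2+2+1+1+1+1 = 8 |
| Composite (subjects) | 2 (15.4%) | 4 (40.0%) | 6 (26.1%) |

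The sums exceed the composite because a subject can appear in more than one row. From rows alone, the number of subjects lies between the largest row and the sum of rows. Above 0.12 mg/kg that is 2 to 6 of 10, or 20% to 60%, around a true 40.0%. The composite came from a custom MedDRA query that included gastritis and urinary tract infection, so membership is not self-evident.

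**5. The same problem for lymphoproliferative disease.** Protocol 4.5.1.3 reports the earlier acute GvHD cases under three labels: 1 EBV-LPD, 1 PTLD and 2 EBV-related lymphoma. Together 1 + 1 + 2 = 4 of 48 (8.3%). Separate rows would not show that total.

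**6. Scale in this trial (illustration).** Assume three rows of 1 in an arm of 8. Each row reads 1/8 = 12.5%. The number of subjects affected could be anything from 1/8 (12.5%) to 3/8 (37.5%), and the rows cannot say which.

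**The case against.** The strongest reply is that the events are counted. The SAP states "AEs will be summarized by the number and percentage of subjects in each primary SOC and preferred term", each subject counts once per term and once per SOC, and section 10.1 presents safety by study drug received. Infections are tabulated by type and organism, serious infections have their own table, and SMQ tables exist to group terms. Every adverse event is also listed by subject in a trial of up to 24, and a PTLD case or a severe cytokine release event would trigger individual review under the stopping rules.

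Most of this stands. A reader might infer that no table counts subjects with malignancy, PTLD, opportunistic infection or cytokine release syndrome. The documents do not support that. Nor do they support calling these events named primary endpoints: protocol Table 2-1 and SAP 4.1 list adverse events, SAEs and clinically significant laboratory, vital-sign and serology changes, but not special-interest events. It is also not certain that the table will go unmade, since SAP 3 allows deviations that are noted in the study report.

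The reply does not restore the group counts. A SOC row counts subjects once but mixes opportunistic with ordinary infections. The SMQ tables name no query. The listings allow a hand count, but only after someone chooses the terms with the data in view. The protocol sentence gives no term list either, so defining the groups falls to the SAP, which under protocol section 12 is to say how variables are derived.

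**Conclusion.** The point holds as a specific, unexplained omission. The SAP drops a summary that its parent protocol commits to, and leaves opportunistic infection and malignancy/LPD/PTLD without a definition. The loss is the pre-defined, once-per-subject count by arm for each risk group. It is clearest for opportunistic infection, next for malignancy/LPD/PTLD, and small for serious infection and cytokine release syndrome. No data are lost, and no hypothesis test is affected because the analysis is descriptive.

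Table 4-1 gives the size: adding rows gives 8 where 6 of 23 subjects were affected, and 6 where 4 of 10 were.

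The conclusion rests on two assumptions: that the redacted part of SAP section 12 contains no special-interest summary, as its headings suggest; and that events in these groups will spread over several terms, as they did in the earlier studies. A secondary inconsistency lies within the protocol: cytokine release syndrome is an example in 12.5.2 but is not on the 10.1.3 list. The change should be made before database lock.

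**What to change.** - Restore the protocol 12.5.2 summary in SAP 10.1.2 as one by-arm table on the Safety Set. Give the number and percentage of subjects with at least one event in each of four groups: serious infection; opportunistic infection including EBV, CMV and BK; malignancy including LPD/PTLD; and cytokine release syndrome, labelled as an identified or potential risk.
- Name the SMQ, custom query or preferred-term list for each group, and fix it before database lock.
- Reconcile the special-interest list in protocol 10.1.3 with the examples in 12.5.2 on cytokine release syndrome.
- If the summary was dropped on purpose, say so in the SAP and give the reason.

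The cost is one extra table and a term list. The protocol already requires these events to be collected and reported, so no new data are needed.
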